T378X5A		Adverse effect of other specified systemic anti-infectives and
		antiparasitics, initial encounter
T378X5D		Adverse effect of other specified systemic anti-infectives and
		antiparasitics, subsequent encounter
T378X5S		Adverse effect of other specified systemic anti-infectives and
		antiparasitics, sequela
T378X6A		Underdosing of other specified systemic anti-infectives and antiparasitics,

ICD-10-CM	Anaphylaxis	Description
		initial encounter
T378X6D		Underdosing of other specified systemic anti-infectives and antiparasitics,
		subsequent encounter
T378X6S		Underdosing of other specified systemic anti-infectives and antiparasitics,
		sequela
T3791XA		Poisoning by unspecified systemic anti-infective and antiparasitics,
		accidental (unintentional), initial encounter
T3791XD		Poisoning by unspecified systemic anti-infective and antiparasitics,
		accidental (unintentional), subsequent encounter
T3791XS		Poisoning by unspecified systemic anti-infective and antiparasitics,
		accidental (unintentional), sequela
T3794XA		Poisoning by unspecified systemic anti-infective and antiparasitics,
		undetermined, initial encounter
T3794XD		Poisoning by unspecified systemic anti-infective and antiparasitics,
		undetermined, subsequent encounter
T3794XS		Poisoning by unspecified systemic anti-infective and antiparasitics,
		undetermined, sequela
T3795XA		Adverse effect of unspecified systemic anti-infective and antiparasitic,
		initial encounter
T3795XD		Adverse effect of unspecified systemic anti-infective and antiparasitic,
		subsequent encounter
T3795XS		Adverse effect of unspecified systemic anti-infective and antiparasitic,
		sequela
T3796XA		Underdosing of unspecified systemic anti-infectives and antiparasitics,
		initial encounter
T3796XD		Underdosing of unspecified systemic anti-infectives and antiparasitics,
		subsequent encounter
T3796XS		Underdosing of unspecified systemic anti-infectives and antiparasitics,
		sequela
T431X5A		Adverse effect of monoamine-oxidase-inhibitor antidepressants, initial
		encounter
T431X5D		Adverse effect of monoamine-oxidase-inhibitor antidepressants,
		subsequent encounter
T431X5S		Adverse effect of monoamine-oxidase-inhibitor antidepressants, sequela
T43215A		Adverse effect of selective serotonin and norepinephrine reuptake
		inhibitors, initial encounter
T43215D		Adverse effect of selective serotonin and norepinephrine reuptake
		inhibitors, subsequent encounter
1432155		Adverse effect of selective serotonin and norepinephrine reuptake
T 40005 4		inhibitors, sequela
143225A		Adverse effect of selective serotonin reuptake inhibitors, initial encounter
143225D		Adverse effect of selective serotonin reuptake inhibitors, subsequent
T422250		encounter
1432255		Adverse effect of selective serotonin reuptake inhibitors, sequela
150901A		Poisoning by unspecified drugs, medicaments and biological substances,
TE0004 D		accidental (unintentional), initial encounter
12030ID		Poisoning by unspecified drugs, medicaments and biological substances,

ICD-10-CM	Anaphylaxis	Description
		accidental (unintentional), subsequent encounter
T50901S		Poisoning by unspecified drugs, medicaments and biological substances,
		accidental (unintentional), sequela
T50904A		Poisoning by unspecified drugs, medicaments and biological substances,
		undetermined, initial encounter
T50904D		Poisoning by unspecified drugs, medicaments and biological substances,
		undetermined, subsequent encounter
T50904S		Poisoning by unspecified drugs, medicaments and biological substances, undetermined sequela
T50905A		Adverse effect of unspecified drugs, medicaments and biological
		substances, initial encounter
T50905D		Adverse effect of unspecified drugs, medicaments and biological
		substances, subsequent encounter
T50905S		Adverse effect of unspecified drugs, medicaments and biological
		substances, seguela
T50906A		Underdosing of unspecified drugs, medicaments and biological
		substances, initial encounter
T50906D		Underdosing of unspecified drugs, medicaments and biological
		substances, subsequent encounter
T50906S		Underdosing of unspecified drugs, medicaments and biological
		substances, sequela
T50991A		Poisoning by other drugs, medicaments and biological substances,
		accidental (unintentional), initial encounter
T50991D		Poisoning by other drugs, medicaments and biological substances,
		accidental (unintentional), subsequent encounter
T50991S		Poisoning by other drugs, medicaments and biological substances,
		accidental (unintentional), sequela
T50994A		Poisoning by other drugs, medicaments and biological substances,
TEODOAD		undetermined, initial encounter
150994D		Poisoning by other drugs, medicaments and biological substances,
TE00046		Undetermined, subsequent encounter
1509945		Poisoning by other drugs, medicaments and biological substances,
		Adverse offect of other drugs, medicaments and hielegical substances

T8089XS		Other complications following infusion, transfusion and therapeutic injection, sequela
T8090XA		Unspecified complication following infusion and therapeutic injection, initial encounter
T8090XD		Unspecified complication following infusion and therapeutic injection, subsequent encounter
T8090XS		Unspecified complication following infusion and therapeutic injection, sequela
T886XXA	х	Anaphylactic reaction due to adverse effect of correct drug or medicament properly administered, initial encounter
T886XXD	х	Anaphylactic reaction due to adverse effect of correct drug or medicament properly administered, subsequent encounter
T886XXS	Х	Anaphylactic reaction due to adverse effect of correct drug or medicament properly administered, sequela

ICD-10-CM	Anaphylaxis	Description
T887XXA		Unspecified adverse effect of drug or medicament, initial encounter
T888XXA		Other specified complications of surgical and medical care, not elsewhere
		classified, initial encounter
T889XXA		Complication of surgical and medical care, unspecified, initial encounter
Y631		Incorrect dilution of fluid used during infusion
Y638		Failure in dosage during other surgical and medical care
Y639		Failure in dosage during unspecified surgical and medical care
Y640		Contaminated medical or biological substance, transfused or infused
Y641		Contaminated medical or biological substance, injected or used for
		immunization
Y651		Wrong fluid used in infusion
Y66		Nonadministration of surgical and medical care
Y69		Unspecified misadventure during surgical and medical care

# EFFECTS OF CODE SEPSIS IMPLEMENTATION ON ED SEPSIS CARE (CODE SEPSIS) STATISTICAL ANALYSIS PLAN

### Objective

Determine the effects of reorganizing emergency department (ED) sepsis care (Code Sepsis protocol) on doorto-antibiotic time for ED patients with sepsis.

### Hypothesis

Early activation of a multidisciplinary, coordinated, team-based assessment and treatment protocol for patients with potential sepsis will decrease door-to-antibiotic time for ED patients with sepsis.

### Study overview

To assess feasibility and test the preliminary effects of ED-based Code Sepsis teams on care delivery and patient outcomes, we will conduct a Phase 2a implementation trial involving Code Sepsis team activation in one ED while collecting contemporaneous control data at two other urban EDs (control sites). Application of pseudo-experimental analysis methods to collected data will facilitate causal inference.

#### Study phases and associated exposures

Dhaca	Detient CD envivel deter	Care received by patients		
Phase	Patient ED arrival dates		Intervention EDs	
Pre-intervention analysis	11/13/2018-11/12/2019	Standard care	Standard care	
Post-intervention wash-in	11/13/2019-2/12/2020	Standard care	Code Sepsis protocol	
Post-intervention analysis	2/13/2020-2/12/2021	Standard care	Code Sepsis protocol	

# Study design

Pragmatic pre/post single-center type III hybrid implementation/effectiveness trial with contemporaneous controls.

# Inclusion/exclusion criteria

Cohort	Inclusion	Exclusion	Cohort eligibility indicator variable*
ED sepsis cohort (primary analysis cohort)	
 
(1) Age ≥18 years
 
(2) Arrival to an intervention or control ED during study period
 
(3) Met all Sepsis-3 criteria in the ED
 
Acute organ failure in the ED defined by SOFA score while in the ED ,≥2 points above baseline
 
Suspected or confirmed infection while in the ED, based on having both: 
 
i. Administration of ,≥1 IV or IV-equivalent antibiotics while in the ED for suspected infection (i.e. antibiotics not given for prophylaxis)
 
ii. Collection of ,≥1 body fluid cultures while in the ED
 
 
 
	
 
Trauma patient
 
Subsequent eligible ED visit with sepsis after first eligible encounter during an analysis window
 
	cohort_sepsis
All adult ED patients cohort	
 
(1) Age ≥18 years
 
(2) Arrival to an intervention or control ED during study period
 
	
 
Trauma patient
 
Received antibiotics within 6 hours prior to study ED arrival
 
Subsequent eligible ED visit after first eligible encounter during an analysis window
 
Left ED without evaluation or treatment
 
	cohort_all
Sepsis high-risk cohort	
 
Age ≥18 years
 
Arrival to an intervention or control ED during study period
 
First recorded temperature ≥38.0°C
 
First-recorded vital sign data meets ≥2 of:         
 
a. Systolic blood pressure <90 mmHg
 
b. Glasgow Coma Scale (GCS) score <15
 
c. Respiratory rate ≥22 breaths/min or oxygen saturation <85%
 
 
 
	
 
Trauma patient
 
Received antibiotics within 6 hours prior to study ED arrival
 
Subsequent eligible ED visit after first eligible encounter during an analysis window
 
Left ED without evaluation or treatment
 
	cohort_risk

Cohort	Inclusion	Exclusion	Cohort eligibility indicator variable*
Sepsis	(1) Age ≥18 years	(1) Trauma patient	cohort_mimics
mimic	(2) Arrival to an intervention or control ED during study period	(2) Received antibiotics	
cohort	(3) Primary ICD-10-CM discharge diagnosis code of venous thromboembolism or congestive heart failure and no ICD- 10-CM discharge diagnosis code for infection in any position	
 
within 6 hours prior to study ED arrival
 
(3) Subsequent eligible ED visit after first eligible encounter during an analysis window
 
(4) Left ED without evaluation or treatment
 
	

\* For analyses including all eligible encounters for a given cohort (i.e., ignoring exclusion criteria #3), the name of the indicator variable is appended with "\_sens" (e.g. "cohort\_sepsis\_sens")

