#### 3.7.1 Primary outcome

Door-to-antibiotic time among all ED sepsis patients. Door-to-antibiotic time is the time from the first recorded arrival time in ED (usually ED triage or registration) and the time the first eligible antibiotic was administered (Appendix A).

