#### 4.2.3 Exclusion criteria:

- Age <18 years
- Trauma patient

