#### 6.5 Variables/data elements

- Patient medical record number(s)
- Patient encounter ID code
- Hospital/facility
- Date of birth
- Age
- Sex
- Race

- Ethnicity
- Marital status
- Preferred language
- Insurance status/type
- Address/zip code (for determination of residence at a nursing facility or other long-term care facility and estimation of socioeconomic status)
- Social Security Number (to assist matching of encounter data to Social Security Death Index and Utah state death records)
- ED disposition
- Hospital disposition
- Date/time of all events related to ED visit and hospitalization (e.g. ED arrival & departure, hospital admission & discharge)
- Date/time antibiotics administered
- Antibiotic utilization
- APACHE II score
- APACHE IV score
- Acute physiology score
- Charlson index
- Elixhauser index
- SOFA score
- Baseline SOFA score over preceding 10 years
- Source of admission (e.g. home, SNF, LTAC, outside hospital)
- Source of infection
- Clinician infection determination, patient illness severity, sepsis status, and agreement with Code Sepsis activation
- Sepsis presence/absence
- Culture results
- Admission diagnosis
- Mode of arrival to ED
- ED triage data including triage acuity score
- Resident involvement in ED care
- Results of all laboratory testing
- Date/time of all laboratory testing
- ED length of stay
- ED vital signs
- ED medications
- ED interventions/procedures
- Date/time, elapsed time, and type of ED events including provider interaction, room placement, disposition
- Date/time of diagnostic testing, vasopressor initiation and other interventions, and management
- Date/time of interventions
- Date/time of blood or body fluid cultures
- Discharge diagnosis and procedure codes
- Billing diagnosis and procedure codes
- Diagnosis-related group
- Hospital length of stay

Code Sepsis I protocol Version 3.0

- In-hospital mortality
- Long-term mortality (e.g. 30d, 90d and 1y mortality)
- Healthcare charges
- ED patient census
- Number of ED beds
- ED patient flow (including counts of patient arrivals, boarding, and admissions)
- Attending physician ED staffing
- Nurse staffing
- Trauma registration status
- Allergies
- Adverse drug reaction events and date/time
- Code Sepsis team activation (Y/N)
- Code Sepsis activation date/time
- Code Sepsis care process completion date/times
- Code Sepsis team function
- Code Sepsis team composition (by role)
- Code Sepsis process adherence

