### **Outcomes & analyses**

Primary outcome

	Analysis		Outcome
Outcome	cohort	Description	variable
Door-to-antibiotic time	Sepsis cohort	Time (minutes) from ED arrival to administration of first IV (or equivalent) antimicrobial while in the ED	abx_elapsed

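### The SAP excludes patients given antibiotics in the 6 hours before arrival from three cohorts but not from the primary sepsis cohort, without a stated reason, so some door-to-antibiotic times can be those of a later dose

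*SAP*

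**What the plan says.** The cohort table under Inclusion/exclusion criteria in the SAP gives the ED sepsis cohort two exclusions: trauma, and "Subsequent eligible ED visit with sepsis after first eligible encounter during an analysis window". The all-adult ED and high-risk cohorts have four, the second being "Received antibiotics within 6 hours prior to study ED arrival". The mimic cohort has the same item ("within 6 hours prior to study ED arrival").

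The table footnote describes the all-encounter version of each cohort as "i.e., ignoring exclusion criteria #3". Its example is the sepsis cohort variable, yet the sepsis row has no third item.

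The SAP defines the primary outcome as "Time (minutes) from ED arrival to administration of first IV (or equivalent) antimicrobial while in the ED". Protocol section 3.7.1 ends the interval at "the time the first eligible antibiotic was administered (Appendix A") and has no rule for a dose given before arrival. Protocol section 4.2.3 excludes only patients under 18 and the category "Trauma patient", so it has no pre-arrival antibiotic exclusion for any cohort.

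**The concern.** The trial asks whether Code Sepsis brings antibiotics forward. If a patient was already treated at another facility, the first dose in the study ED is a repeat or an added drug, and nothing done in that ED can make the true first dose earlier. Such patients stay in the primary analysis, and in the secondary outcome of antibiotics within 3 hours, but are removed from the other three cohorts.

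Neither the adjustment list nor the propensity list in the SAP includes pre-arrival antibiotics or transfer from another hospital. Ambulance arrival and long-term-care origin are included but do not identify pre-treatment. The protocol plans to record "Source of admission (e.g. home, SNF, LTAC, outside hospital"), so transfers can be identified. At stake are a diluted or noisier estimate and, under a further condition worked out below, a biased one.

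**Working it through.** **Cohort comparison**

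| SAP cohort | Exclusion 1 | Exclusion 2 | Exclusion 3 | Exclusion 4 |
|---|---|---|---|---|
| Sepsis (primary) | trauma | repeat visit | none | none |
| All adult ED | trauma | antibiotics before arrival | repeat visit | left without evaluation |
| High-risk | trauma | antibiotics before arrival | repeat visit | left without evaluation |
| Mimic | trauma | antibiotics before arrival | repeat visit | left without evaluation |

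The missing fourth item does no harm in the sepsis row, because cohort entry already requires an ED antibiotic. The missing pre-arrival item is not redundant in that way. The footnote's #3 fits the sepsis row only if an item once stood between trauma and repeat visit.

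**The plan's own power figure**

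Inputs (protocol section 7.3; SAP, Power): 1,650 sepsis patients a year at the intervention ED, 2,200 at the controls, SD 75 minutes, target 16 minutes, stated power 90%. Each analysis phase lasts one year. Two-sided 5% is assumed, since the SAP does not state sidedness.

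- SE = sqrt(2 × 75²/1,650 + 2 × 75²/2,200) = sqrt(6.82 + 5.11) = 3.45 minutes.
- Power = Φ(16/3.45 − 1.96) = 99.6%. The change detectable with 90% power is (1.96 + 1.28) × 3.45 = 11.2 minutes.
- The stated 90% is approximated only if the annual counts are read as totals over both phases (825 and 1,100 per cell), which gives 90.6%. The plan's figure came from simulations whose details are not given and may be deliberately conservative. Both starting points are carried forward.

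**Bias from keeping pre-treated patients**

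Let p be the pre-treated share in a site-by-period cell, and g the mean ED time of pre-treated minus other patients. Each cell mean then shifts by p × g. With g constant, the shift in β3 is

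g × [(change in p at the intervention site) − (change in p at the control sites)].

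A stable difference in p between sites cancels. Neither p nor g is in the documents, so the following values are assumed:

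| Differential change in share | g = 60 min | g = 120 min |
|---|---|---|
| 0 points | 0 | 0 |
| 1 point | 0.6 | 1.2 |
| 2 points | 1.2 | 2.4 |
| 5 points | 3.0 | 6.0 |

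A negative g, with transfers re-dosed faster than other patients, reverses the sign. If instead p is stable and g changes differently between sites, the shift is p × that differential change. For example, 0.05 × 60 = 3.0 minutes, within the same range. All of this is on the additive minute scale in which the 16-minute target is stated.

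**Cost of excluding them**

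Dropping a fraction f from every cell multiplies the SE by 1/sqrt(1 − f). The base is 2 × (1,650 + 2,200) = 7,700 patients.

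| Assumed f | Patients left | Power for 16 min, stated inputs | Power, starting from the stated 90% |
|---|---|---|---|
| 2% | 7,546 | 99.6% | 89.4% |
| 5% | 7,315 | 99.5% | 88.5% |
| 10% | 6,930 | 99.3% | 86.8% |
| 20% | 6,160 | 98.6% | 82.6% |

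**The case against.** The sepsis cohort follows the protocol, which sets no such exclusion and measures the outcome among all ED sepsis patients in a pragmatic, intention-to-treat design. The other cohorts have outcomes about whether antibiotics were given, which a pre-arrival dose contaminates directly, whereas an ED antibiotic is a condition of entry to the sepsis cohort. The difference may therefore be deliberate. Entry also requires an antibiotic and a culture in the study ED, so transfers who are not dosed and cultured again never enter. The quoted exclusion names no route, so for a patient whose earlier dose was not IV or equivalent, the ED dose is still the first eligible one.

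All of this stands. It is a fair argument for keeping the protocol-defined cohort as primary, but the SAP does not make it, and it does not explain the footnote.

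A reader might go further in four ways that the documents do not support:

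- **That the outcome is mismeasured.** It is defined as the first dose in the ED, and that is what is recorded. The issue is what the estimate represents.
- **That no door-to-antibiotic analysis leaves these patients out.** The SAP repeats the primary analysis among high-risk patients who received ED antibiotics, and that cohort has the exclusion. It is a narrower population, so it does not settle the question for the primary cohort.
- **That the tertiary intervention site makes bias likely.** Protocol Table 1 describes both control hospitals as regional referral centres, and a stable difference between sites is absorbed by the site term. A post phase in 2020–21 makes some shift in case mix plausible, but nothing shows that it differed by site.
- **That the planned effect of 30% × (170 − 50) = 36 minutes should be scaled down by the pre-treated share.** The 30% activation rate already averages over all sepsis patients, so this may count the dilution twice.

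**Conclusion.** The inconsistency is real and unexplained, and it sits in the cohort that carries the primary outcome. Retaining re-dosed patients adds noise or dilution. Bias in β3 needs a differential change between sites in the pre-treated share or the timing gap. Under the assumed ranges it is 0 to about 6 minutes in either direction. The upper end is 6/16 = 38% of the target difference and 6/3.45 = 1.7 standard errors, and it needs both the largest assumed imbalance and the largest assumed gap. The documents support neither value, so no claim is made that the estimate will be biased.

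The footnote numbering suggests a dropped line but does not prove one. Loss of an item when the PDF was read cannot be fully ruled out, although the two-item list reads as complete. This is a low-cost improvement that protects the primary estimate. It does not invalidate the plan.

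**What to change.** - Add the 6-hour pre-arrival antibiotic exclusion to the sepsis cohort for door-to-antibiotic time, and report the cohort without it as a sensitivity analysis. If the protocol-defined cohort is kept as primary, state why and prespecify the excluded version as the sensitivity analysis.
- State how a dose given before arrival is handled in the outcome definition.
- Correct the footnote so that it names the repeat-visit exclusion rather than a number.

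The cost is a few lines in the SAP and one further model run. The criterion is already defined for three cohorts, and it is fixed before ED arrival, so excluding on it does not select on anything Code Sepsis could influence. The downside is slightly fewer patients, with the small loss of power shown above.

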### Primary exposure

The primary exposure is arrival to the ED at the intervention hospital during the post-intervention analysis period rather than the pre-intervention analysis period.

Exposure parameter	Description	Exposure variable
Intervention site	Presentation to ED at intervention or control hospital	intervention_site
Analysis phase	Presentation to ED during pre-intervention analysis period or post-intervention analysis period. Encounters presenting during the wash-in period have a missing variable for this variable.	analysis_phase (value missing if wash-in period)
Study phase	Presentation to ED during pre-intervention analysis period, wash-in period, or post-intervention analysis period. This variable is not used for primary differences-in-differences analyses.	study_phase

### **Outcomes & analyses**

Primary outcome

	Analysis		Outcome
Outcome	cohort	Description	variable
Door-to-antibiotic time	Sepsis cohort	Time (minutes) from ED arrival to administration of first IV (or equivalent) antimicrobial while in the ED	abx_elapsed

